### 5. OUTCOMES

#### 5.1 Definitions

##### 5.1.1 Primary Outcome

The primary outcome will be the absolute change in the Sequential Organ Failure Assessment (SOFA) score from enrollment (time=0) to 72 hours after drug administration. The SOFA score will be defined using a modification in which the SaO2/FiO2 ratio is substituted for the PaO2/FiO2 ratio as has been previously described. This modified score will be used so that participants without an existing arterial catheter can be spared arterial puncture.

Points	SaO 2 */FiO 2 §	Blood Pressure	GCS 	Bilirubin (mg/dL)	Creatinine (mg/dL)	Platelets (x10  µL)
1	<400	< 70 mm/Hg	13–14	1.2–1.9	1.2 – 1.9	<150
2	<326	dopamine ≤ 5 µg/kg/min or dobutamine (any dose)	10–12	2–5.9	2.0 – 3.4	<100
3	<236 (and receiving invasive or non-invasive mechanical ventilation)	dopamine > 5µg/kg/min, epinephrine/norepinephrine ≤ 0.1 µg/kg/min	6–9	6–11.9	3.5 – 4.9 Or UOP † <500ml/day	<50
4	<151 (and receiving invasive or non-invasive mechanical ventilation)	dopamine > 15, epinephrine/norepinephrine > 0.1 µg/kg/min	<6	>12	> 5.0 UOP † <200ml/day Or receiving renal replacement therapy	<20

\*SaO2=Oxygen saturation (%); § = Fraction of inspired oxygen (%); || = Glasgow Coma Scale; † = Urine Output

FiO2 will be determined by using either the set FiO2 (for patients receiving invasive or non-invasive mechanical ventilation) or by adding 3% FiO2 for each liter/minute of supplemental oxygen added up to 100% FiO2 (for patients not receiving mechanical ventilation). Patients with an SaO2/FiO2 ratio <236 who are not receiving invasive or non-invasive mechanical ventilation, will be assigned a score of 2.

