#### **3.3 Exclusion criteria**

Exclusion criteria:

- 1) Member of a protected population (pregnant, prisoner)
- 2) Known history of kidney stones within the past 1 year (not including incidentally noted stones noted on imaging studies)
- 3) End stage renal disease requiring dialysis (hemodialysis or peritoneal dialysis)
- 4) Known history of G6PD deficiency
- 5) Known history of Hemochromatosis
- 6) Comfort Measures Only status
- 7) Anticipated death within 24-hours despite maximal therapy (as determined by the enrolling physician)
- 8) Receiving supplemental vitamin B1 in a dose greater than that contained in a multivitamin (<2mg)
- 9) Clinical indication for steroids (e.g. chronic use) as determined by the clinical team providing this drug
- 10) Clinical indication for ascorbic acid supplementation in any form
- 11) Clinical indication for vitamin B1 as determined by the clinical team providing this drug
- 12) Known allergy to vitamin C, hydrocortisone, or vitamin B1

Justification of Inclusion and Exclusion Criteria: The inclusion criteria were chosen to isolate a septic participant population with high risk of organ injury and death. The exclusion criteria were chosen to minimize the risk of potential harm and to ensure that participants enrolled do not already have chronic end-stage renal failure with a high likelihood of early need for renal replacement therapy. By evaluating this high-risk population (i.e., most likely to die), we will target those most likely to benefit and therefore increase the probability of showing efficacy.

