##### **4.3 Randomization**

After consent is obtained, the research team will notify the local research pharmacy. The research pharmacy will be in possession of the randomization list and will determine which arm (intervention vs. placebo) the participant will be enrolled in.

Patients should be randomized, consented, and enrolled in the study as soon as possible after meeting inclusion criteria. Patients should not be *consented* if it has been >24hours since the patient met inclusion criteria (i.e. start of vasopressors). At the time of randomization and study drug administration, the patient should still be receiving a vasopressor. The patient should not be given study drug if the vasopressor has been stopped (e.g. patient met inclusion criteria overnight but could not be consented for logistical reasons and then improves to the point of no longer requiring a vasopressor). In this scenario, the patient will be entered into the database as consented but not enrolled.

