### 6.2.2 SOFA score and renal failure

The change in SOFA score will be calculated and compared between groups using the Wilcoxon Rank Sum test (if the change is not normally distributed) or by a t-test if the change is approximately normally distributed. Fisher's exact tests will be used to compare the incidence of renal failure during the index ICU stay.

If a participant expires prior to the 72-hour time point, SOFA scores will be imputed based on a pre-defined plan as follows. If a participant expires before 24-hours has elapsed, a 20% increase from baseline will be imputed. If a participant expires between 24-hours and 48-hours, a 15% increase from the 24-hour time point will be imputed. If a participant dies between 48-hours and 72-hours, a 20% increase from the 24-hour time point will be imputed. Sensitivity analyses will be performed using various other imputation techniques. Specifically, we will perform 1) a sensitivity analysis in which the worst possible SOFA score (score of 24) is imputed for those participants who expire, 2) a sensitivity analysis in which the last SOFA score for participants who expire will be carried forward, and 3) a sensitivity analysis in which only those patients who survive to 72-hours are included. These sensitivity analyses were chosen to model 'worst-possible' and 'best-possible' scenarios. For the secondary outcome of renal failure, participants who expire during their ICU stay will be assessed to have developed renal failure if they demonstrated any degree of unresolved KDIGO acute kidney injury prior to death. If there was no evidence of acute kidney injury prior to death or if kidney injury had fully resolved, these participants will be assessed as not having developed renal failure.

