### 684 *6.2.2 SOFA score and renal failure*

685 The change in SOFA score will be calculated and compared between groups using the Wilcoxon  
686 Rank Sum test (if the change is not normally distributed) or by a t-test if the change is approximately  
687 normally distributed. Fisher’s exact tests will be used to compare the incidence of renal failure  
688 during the index ICU stay.

689

690 If a participant expires prior to the 72-hour time point, SOFA scores will be imputed based on a pre-  
691 defined plan as follows. If a participant expires before 24-hours has elapsed, a 20% increase from  
692 baseline will be imputed. If a participant expires between 24-hours and 48-hours, a 15% increase  
693 from the 24-hour time point will be imputed. If a participant dies between 48-hours and 72-hours, a  
694 20% increase from the 24-hour time point will be imputed. Sensitivity analyses will be performed  
695 using various other imputation techniques. Specifically, we will perform 1) a sensitivity analysis in  
696 which the worst possible SOFA score (score of 24) is imputed for those participants who expire, 2) a  
697 sensitivity analysis in which the last SOFA score for participants who expire will be carried forward,  
698 and 3) a sensitivity analysis in which only those patients who survive to 72-hours are included.  
699 These sensitivity analyses were chosen to model ‘worst-possible’ and ‘best-possible’ scenarios. For  
700 the secondary outcome of renal failure, participants who expire during their ICU stay will be  
701 assessed to have developed renal failure if they demonstrated any degree of unresolved KDIGO  
702 acute kidney injury prior to death. If there was no evidence of acute kidney injury prior to death or if  
703 kidney injury had fully resolved, these participants will be assessed as not having developed renal  
704 failure.

705

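### A participant moved to comfort care before 72 hours and still alive then is scored from values after support is withdrawn, and can count as improved on the primary outcome

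*Protocol*

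**What the plan says.** **Outcome.** Protocol 5.1.1: "The primary outcome will be the absolute change in the Sequential Organ Failure Assessment (SOFA) score from enrollment (time=0) to 72 hours after drug administration".

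**Scoring.** Several items in the 5.1.1 table depend on support being given.
- Respiratory 4 needs a ratio of "<151 (and receiving invasive or non-invasive mechanical ventilation"; respiratory 3 needs a ratio below 236 and ventilation. Participants below 236 "who are not receiving invasive or non-invasive mechanical ventilation, will be assigned a score of 2".
- Cardiovascular 3 is defined by what is running: "dopamine > 5µg/kg/min, epinephrine/norepinephrine ≤ 0.1 µg/kg/min". Score 4 uses higher doses of the same drugs, and score 2 uses low-dose dopamine or any dobutamine. With no listed drug the most available is 1, for low blood pressure.
- Renal replacement therapy gives renal 4, as do high creatinine or very low urine output.

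**Baseline.** Protocol 4.3: "At the time of randomization and study drug administration, the patient should still be receiving a vasopressor".

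**Deaths.** Protocol 6.2.2: "If a participant expires prior to the 72-hour time point, SOFA scores will be imputed based on a pre-defined plan as follows". The rules are baseline plus 20% for death before 24 hours, the 24-hour score plus 15% for death at 24 to 48 hours, and the 24-hour score plus 20% for death at 48 to 72 hours. The SAP has the same trigger in its 6.2.2: "If a participant expires prior to the 72-hour time point, SOFA scores will be imputed". Three sensitivity analyses follow: a score of 24 for those who die, last score carried forward for those who die, and survivors to 72 hours only.

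**Comfort care.** "Comfort Measures Only status" is an exclusion in 3.3. Neither 4.4.1 (contingencies) nor 6.2.2 mentions a transition to it after enrollment.

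**The concern.** The table cannot tell support stopped because the patient recovered from support stopped because the goal of care changed. Section 6.2.2 treats early death as worsening, but a participant in the same clinical position who is still breathing at hour 72 falls outside it. Whether treatment failure is recorded as worse or as better then depends on which side of hour 72 death falls.

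No analysis in the plan corrects this. The first two sensitivity analyses concern participants who die, and the third keeps everyone alive at 72 hours. If 72-hour laboratory tests are not drawn, the score is missing, and 6.2.2 has no rule for a missing score in a living participant.

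At stake is a bias in the primary comparison that favours whichever arm has more such transitions. If transitions follow mortality, that is the arm doing worse.

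**Working it through.** **1. The plan's own figure (6.1).** Inputs: difference 2, SDs 4 and 2, 100 per arm, two-sided alpha 0.05.
- SE = √(16/100 + 4/100) = √0.20 = 0.447.
- Power = Φ(2/0.447 − 1.96) = Φ(2.51) = 0.994. The unequal-variance t calculation (145.6 df) gives 0.9935.
- The stated power above 99% is reproduced.

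**2. Score change on withdrawal of ventilator and scored vasopressor (5.1.1).** Afterwards respiratory is taken as 2, and cardiovascular as 1 (pressure below 70) or 0.

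| Baseline respiratory/cardiovascular | Change, other organs unchanged | Change if coma item also worsens by 4 (pressure below 70) |
|---|---|---|
| 3/3 | −3 to −4 | +1 |
| 4/3 or 3/4 | −4 to −5 | 0 |
| 4/4 | −5 to −6 | −1 |

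Three qualifications apply.
- Being ventilated does not by itself give respiratory 4. A ventilated participant with a ratio of 236 to 325 scores 2 and may score 2 afterwards. From cardiovascular 4 the loss is then only the cardiovascular 3 to 4 points.
- Two is a cap off the ventilator, not a floor. If room air is taken as 21% (an assumption), a saturation of 70% gives 70/0.21 = 333, which scores 1.
- Phenylephrine, vasopressin and angiotensin II qualify for entry in 3.2 but have no row in the table, so stopping one of these alone changes nothing.

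**3. The same participant under the death rule (6.2.2).** Illustration: baseline 12 = respiratory 4 + cardiovascular 4 + other organs 4, with an unchanged 24-hour score.

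| Course | 72-hour score | Change |
|---|---|---|
| Comfort care, alive at 72 h, pressure below 70 | 2 + 1 + 4 = 7 | −5 |
| Death before 24 h | 12 × 1.20 = 14.4 | +2.4 |
| Death at 24 to 48 h | 12 × 1.15 = 13.8 | +1.8 |
| Death at 48 to 72 h | 12 × 1.20 = 14.4 | +2.4 |
| Death, worst-score sensitivity analysis | 24 | +12 |

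The gap between the first row and a +2.4 imputation is 7.4 points. With the full coma offset (change −1) it is 3.4.

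**4. Effect on the arm difference.** Shift = between-arm imbalance in such participants × mis-score per participant. The documents give no frequency, so the imbalances are assumptions.

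| Mis-score | 1 percentage point | 3 percentage points |
|---|---|---|
| 3.4 (full coma offset) | 0.03 | 0.10 |
| 5 (spurious fall alone) | 0.05 | 0.15 |
| 7.4 (against +2.4 death imputation) | 0.07 | 0.22 |

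The largest, 0.22, is 0.22/2 = 11% of the planned difference. If it runs against treatment, power under the design SDs falls from 99.4% to 97.8%.

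**The case against.** The case against is mostly about size, and much of it stands.

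- **Narrow window.** Patients already in comfort care or expected to die within 24 hours are excluded at entry. Those who die before 72 hours are already imputed. Later deaths still count in 30-day mortality. An imbalance of 3 percentage points would be 15% of the planned 20-point mortality difference (40% against 20%).
- **Offsets.** A falling coma score can cancel most of the drop. Stopping renal replacement need not lower the renal item, because creatinine or urine output can hold it at 4.
- **Direction.** No document says transitions will differ by arm. If they are equally frequent, the result is noise or dilution. With no true effect on survival or transitions no imbalance is expected, so an inflated false-positive rate does not follow.
- **Choice of estimand.** Using the observed 72-hour score is a possible choice. The plan does not say it has made that choice, and its handling of deaths points the other way.

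A reader might infer that every ventilated participant on a high vasopressor dose loses at least 5 points. The table does not support that: the certain part is the cardiovascular 3 to 4 points, and respiratory may lose nothing. A reader might also infer that the planned effect could be reversed. At 7.4 points per participant that needs an imbalance of 2/7.4 = 27 percentage points, more than the whole planned mortality difference.

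None of this supplies the missing rule.

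**Conclusion.** The point holds as a defect in a stated rule. Followed exactly, the plan can record a participant withdrawn to comfort care and alive at 72 hours as improved, while scoring the same participant as worsened had death come earlier. From 4/4 the per-participant error is 5 to 6 points before any offset, or 7.4 against a +2.4 death imputation in the illustrated case.

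The trial-level bias is unknown. Under assumed imbalances of 1 to 3 percentage points it is about 0.05 to 0.2 SOFA points on a planned difference of 2, and smaller where coma scores worsen. It favours the arm with more transitions. This does not threaten the design, but it should be corrected because the remedy is cheap and is best settled before allocation is known.

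**What to change.** Add a paragraph to 6.2.2 in both documents:

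- For participants changed to comfort care before 72 hours, do not score SOFA from values after withdrawal of support. Apply the existing death imputation for the interval in which the transition occurred, with the reference score that rule already uses (baseline or 24-hour).
- Treat them like deaths in the worst-score, last-score-carried-forward and survivors-only sensitivity analyses. The score carried forward should be the last one before the transition.
- Report the number of such participants in each arm.
- Add a sensitivity analysis using the observed 72-hour scores.

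Record the date and time of the transition on the CRF, if not already captured; the CRF is a separate document and could not be checked.

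The cost is one paragraph and at most one CRF field. The downside is that a few observed scores are replaced by imputed ones, sometimes built on a 24-hour score up to two days old; the observed-score analysis shows how much that matters. The change concerns scoring only and alters no clinical care.

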##### 5.1.2 Key Secondary Outcomes

Incidence of Acute Renal Failure – Renal failure will be defined as the development of Kidney Disease Improving Global Outcomes [KDIGO] Stage 3 acute kidney injury during the index ICU stay after study enrollment.

KDIGO Stage	Serum creatinine criteria	Urine output criteria
1	Increase in serum creatinine of more than or equal to 0.3 mg/dl ( $\geq$ 26.4 $\mu$ mol/l) or increase to more than or equal to 150% to 200% (1.5- to 2-fold) from baseline	Less than 0.5 ml/kg per hour for more than 6 hours
2	Increase in serum creatinine to more than 200% to 300% (> 2- to 3-fold) from baseline	Less than 0.5 ml/kg per hour for more than 12 hours
3	Increase in serum creatinine to more than 300% (> 3-fold) from baseline (or serum creatinine of more than or equal to 4.0 mg/dl [<math>\geq</math> 354 <math>\mu</math>mol/l]) with an acute increase of at least 0.5 mg/dl [44 <math>\mu</math>mol/l])	Less than 0.3 ml/kg per hour for 24 hours or anuria for 12 hours OR New renal replacement therapy (RRT)

**30-Day Mortality** – Mortality at 30-days. This will be assessed by review of the medical records if the participant remains in the hospital or if the participant expired while in the hospital. If the participant was discharged, 30-day mortality will be assessed by contacting the participant by phone or by searching the National Center for Health Statistics (NCHS) National Death Index (NDI) consistent with a recent multicenter phase III trial in sepsis. Phone calls will be made by the research team at each site.

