### **1.3 The combination of vitamin C, hydrocortisone, and vitamin B1 may improve outcomes**

In a before-and-after study exploring the effects of the combination of vitamin C, hydrocortisone, and vitamin B1 in a cohort of participants with sepsis and septic shock, Marik et. al. found a remarkable improvement in time to shock reversal ( $18.3 \pm 9.8$  hours vs.  $54.9 \pm 28.4$  hours), organ injury ( $\Delta$ SOFA  $4.8 \pm 2.4$  vs.  $0.9 \pm 2.7$ ), and mortality (8.5% vs. 40.4%) following implementation of the drug 'cocktail' as compared to before implementation even after adjusting for potential confounders. This study joins other promising trials of individual elements of this drug combination. In a trial of vitamin B1 in septic shock, there was a substantial reduction in mortality and organ injury (particularly kidney injury) in those with vitamin B1 deficiency and septic shock who were given vitamin B1 as compared to placebo. In addition, several studies of vitamin C alone have shown promise in critically ill populations and a recent meta-analysis of corticosteroids in sepsis suggests potential benefit.

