## 5.3 Additional Secondary Outcomes

### 5.3.1 Additional secondary outcomes

Additional secondary outcomes will include length of ICU stay, length of hospital stay, ventilator-free days over the first 7-days after enrollment, shock-free days over the first 7-days after enrollment,

and the incidence of delirium on day #3 of the ICU stay (as assessed using the Confusion Assessment Method [CAM-ICU] system). Sites at which the CAM-ICU is performed daily as part of standard-of-care should assess whether delirium occurs on any day during the initial ICU stay. See Appendix #2.

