### 6.2.4 Additional Secondary Analyses

Both ICU and hospital length of stay will be compared using Wilcoxon Rank Sum tests. Ventilator and shock free days over the first 7-days after enrollment will likewise be compared using the Wilcoxon Rank Sum given that the data will likely be not normally distributed. In these latter two analyses, patients who expire prior to 7-days will be assessed to have 0 ventilator or shock free days if they had died while on a ventilator or vasopressor respectively. The incidence of delirium will be compared using the Fisher's exact test. For the quality-of-life outcome (i.e. 90-day SF-36), the primary analysis will only include patients with available data. As a secondary analysis, multiple imputation will be used to estimate SF-36 scores in all patients not known to be dead at 90 -days.

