#### 529 5.1.2 Key Secondary Outcomes

530 Incidence of Acute Renal Failure – Renal failure will be defined as the development of Kidney  
 531 Disease Improving Global Outcomes [KDIGO] Stage 3 acute kidney injury during the index ICU stay  
 532 after study enrollment.  
 533

KDIGO Stage	Serum creatinine criteria	Urine output criteria
1	Increase in serum creatinine of more than or equal to 0.3 mg/dl (≥ 26.4 µmol/l) or increase to more than or equal to 150% to 200% (1.5- to 2-fold) from baseline	Less than 0.5 ml/kg per hour for more than 6 hours
2	Increase in serum creatinine to more than 200% to 300% (> 2- to 3-fold) from baseline	Less than 0.5 ml/kg per hour for more than 12 hours
3	Increase in serum creatinine to more than 300% (> 3-fold) from baseline (or serum creatinine of	Less than 0.3 ml/kg per hour for 24 hours or anuria for 12 hours OR

	more than or equal to 4.0 mg/dl [ $\geq$ 354 $\mu$ mol/l] with an acute increase of at least 0.5 mg/dl [44 $\mu$ mol/l])	New renal replacement therapy (RRT)
--	--	-------------------------------------

534

535 30-Day Mortality – Mortality at 30-days. This will be assessed by review of the medical records if the  
536 participant remains in the hospital or if the participant expired while in the hospital. If the participant  
537 was discharged, 30-day mortality will be assessed by contacting the participant by phone or by  
538 searching the National Center for Health Statistics (NCHS) National Death Index (NDI) consistent  
539 with a recent multicenter phase III trial in sepsis. Phone calls will be made by the research team at  
540 each site.

541

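### Renal failure is counted only until ICU exit, so any difference in ICU stay between arms can distort a key secondary outcome; a fixed-window companion analysis should be pre-specified

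*Protocol*

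**What the plan says.** Protocol 5.1.2 defines renal failure as KDIGO "Stage 3 acute kidney injury during the index ICU stay after study enrollment". SAP 5.1.2 has the same definition: "KDIGO] Stage 3 acute kidney injury during the index ICU stay". No number of days is attached; the window closes when the participant leaves the ICU.

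Protocol 6.2.2 states that Fisher's "exact tests will be used to compare the incidence of renal failure during the index ICU stay". The same section gives one rule for a window that ends early, for deaths: "participants who expire during their ICU stay will be assessed to have developed renal failure if they demonstrated any degree of unresolved KDIGO" (that is, kidney injury of any stage still present at death). All other ICU deaths are non-events. Neither document says how to treat a participant who leaves the ICU alive. There is no common horizon, no competing-risk analysis and no sensitivity analysis for unequal stay.

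ICU stay is itself an outcome. Protocol 5.3.1 says "Additional secondary outcomes will include length of ICU stay, length of hospital stay" among others, and 6.2.4 says "Both ICU and hospital length of stay will be compared using Wilcoxon Rank Sum tests". The rationale in Protocol 1.3 rests on a before-and-after study that "found a remarkable improvement in time to shock reversal": 18.3 versus 54.9 hours.

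**The concern.** A proportion with an event is comparable between arms only if both arms are observed in the same way. Here the length of observation is set by ICU exit, which happens after randomization and which the trial itself compares by arm. A participant who leaves on day 3 and develops Stage 3 injury on the ward on day 5 is a non-event; the same injury in someone still in the ICU is an event. The death rule adds to this dependence on location. An ICU death with any unresolved kidney injury, even Stage 1, counts as renal failure, while a ward death with the same injury does not.

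Protocol 5.2 argues that a kidney benefit could alter practice on its own, and 6.1 gives the outcome its own power calculation. If the arms differ in ICU stay, the planned test cannot say how much of a renal difference is kidney protection and how much is unequal observation.

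**Working it through.** **The plan's own figure.** Inputs from Protocol 6.1 and 6.2.1: 30% versus 55% renal failure, 100 per arm, two-sided alpha 0.05, Fisher's exact test. Full enumeration of the exact test gives 93.9% power, which reproduces the stated 94%. With 55% in both arms and equal windows, the test rejects in 3.9% of trials. The sample-size arithmetic is not in question.

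**Illustration of unequal windows.** The documents give no ICU stay and no timing of Stage 3 injury, so these are assumptions:
- ICU stay T is lognormal with log SD 0.8, median 5 days on placebo and 4.5, 4 or 3 days on treatment.
- The renal hazard is identical in both arms (no true effect), with cumulative hazard c·t^k. k = 1 is a constant hazard; k = 0.5 and 0.3 put events progressively earlier.
- Observed incidence is the average of 1 − exp(−c·T^k) over T. c is set so that placebo gives 55%: c = 0.155, 0.352 and 0.490 for k = 1, 0.5 and 0.3.
- Deaths are not modelled.

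Apparent incidence on treatment, with the two-sided Fisher rejection rate at 100 per arm in brackets:

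| Hazard shape | 5 vs 4.5 days | 5 vs 4 days | 5 vs 3 days |
|---|---|---|---|
| k = 1 (constant) | 52.0% (6%) | 48.6% (13%) | 40.7% (49%) |
| k = 0.5 | 53.2% (5%) | 51.3% (7%) | 46.6% (19%) |
| k = 0.3 | 53.9% (4%) | 52.7% (5%) | 49.7% (10%) |

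The spurious difference from 55% runs from 2.3 points (55 − 52.7) to 6.4 points (55 − 48.6) for a 4-day treated median, and from 5.3 to 14.3 points for a 3-day one.

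**Cross-check with a different model.** Take exponential ICU exit and a constant hazard, with treated ICU time at a ratio r of placebo. The treated odds of an event are then r × 0.55/0.45.
- r = 0.8: odds 0.978, incidence 49.4%, rejection 10.5%.
- r = 0.5: odds 0.611, incidence 37.9%, rejection 64.5%.

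If only 25% of placebo events come late enough to depend on the window, the same ratios give 52.8% (rejection 4.9%) and 49.0% (11.5%). If only 10% are late, r = 0.5 gives 52.4% (5.3%).

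Both models show the same thing: the distortion is small when Stage 3 injury comes early or stays are similar, and large only when late events are common and stays differ a good deal.

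**The case against.** **Expected shortening.** A reader might infer that the trial expects treatment to shorten ICU stay. The documents do not say so. ICU stay is listed without a direction or a figure, and the hours quoted in 1.3 are for shock reversal, not ICU days. What stands is that ICU stay may change and is tested for change.

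**Fixed direction.** A reader might also infer that the bias must favour treatment. Protocol 6.1 plans on mortality falling from 40% to 20%; preventing early ICU deaths could lengthen observation on treatment and push the other way. The illustration contains no deaths, so its direction follows from the assumed shorter stay. Some of the 55% could also be assigned by the death rule rather than by days observed.

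**Size.** The constant-hazard row is an upper extreme. It keeps the ICU hazard running after discharge, although participants leave because they are recovering, and implies 1 − exp(−0.155 × 7) = 66% with Stage 3 injury by day 7. Protocol 4.3 allows consent only within 24 hours of meeting inclusion criteria and requires a vasopressor at study drug administration, which makes early injury more credible. A half-day difference gives only 4–6% rejection.

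**Detectability.** ICU stay by arm will be reported, and the 72 h SOFA score contains a renal component. That would reveal unequal windows, but the plan has no renal analysis that removes their effect.

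**Consistency within the protocol.** This is not the only outcome without a fixed window. Delirium at sites with daily assessment covers any day of the initial ICU stay (5.3.1), and new infection has no stated window (5.4.2).

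**Conclusion.** The point holds in a limited form. Followed exactly, the plan lets the observation time for a key secondary outcome depend on a post-randomization event, with no rule for live ICU exit and no analysis that would show the consequence. Neither the direction nor the size of any bias can be derived from the documents. Under the stated assumptions, rejection with no renal effect is about 5–13% for 5 versus 4 days and about 10–49% for 5 versus 3 days, against 3.9% with equal windows. The 49% should not be read as the trial's likely false-positive rate; it needs a 40% cut in median stay (2/5) together with a constant hazard.

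The primary SOFA outcome and the 94% power statement are unaffected. The flaw does not require the ICU-stay definition to be dropped, but a companion analysis is cheap enough that it should be added.

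**What to change.** Keep the ICU-stay definition if the sponsor prefers it, and add to 6.2.2 in both documents a pre-specified companion analysis:

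- Count creatinine-defined KDIGO Stage 3 injury or new renal replacement therapy from enrollment through one fixed time common to all participants, whether in the ICU, on the ward or readmitted.
- Use 120 h if the analysis is to rest on scheduled samples: Protocol 4.5 draws creatinine at 0, 24, 72 and 120 h in all participants. Day 7 would match the ventilator- and shock-free day window but needs chart creatinine beyond the last scheduled sample.
- State one rule for deaths inside the window and apply it regardless of location.
- Report the result beside the ICU-stay result and ICU length of stay by arm, and interpret any kidney claim from the three together.

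Cost: some record abstraction for renal replacement therapy after ICU exit. Protocol 7.1 already takes most variables from the electronic record. The companion loses the urine-output criteria, which cannot be relied on outside the ICU, and a 120 h window misses later events. If the 30% and 55% rates also held in a fixed window, power would stay at 93.9%; the documents give no fixed-window rates to test that.
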